11.1. Pharmacokinetic Concentration Presentation

Serum concentration data (unit: ng/mL) will be summarized on the POE analysis population by visit and by dosing regimen from Baseline and Week 24, using the following statistics: arithmetic mean, SD, coefficient of variation (CV), geometric mean, geometric CV, median, minimum, maximum, 95% CI of the arithmetic mean, and number below the limit of quantification (BLQ).

Mean and individual (spaghetti plot) serum concentration(s) will be plotted by visit and by dosing regimen on both a linear and semi-logarithmic scale on the POE analysis population (2 plots).

Individual serum concentrations will be listed on the POE analysis population.

This document is confidential.

12. Immunogenicity

Blood samples to assess anti-Nemolizumab ADA will be collected at Baseline, Week 24 and Early Termination. Immunogenicity analyses will be summarized on the POE analysis population.

Details related to the processing of serum samples and the assessments of ADA will be described in the bioanalytical plan, which will be finalized before the beginning of sample analysis. Results will be described in the bioanalytical report, which will be included as an appendix in the final clinical study report.

Incidence of positive ADA results will be summarized (absolute occurrence and percent of subjects) and plotted by dosing regimen at each visit. The concentration of ADA titer (ng/mL) and neutralizing antibodies (ng/mL) will be summarized as continuous variables.

The number and percentage of subjects with treatment related ADA will be summarized by visit and dosing regimen. A treatment-related ADA is defined when the Baseline or confirmatory ADA result is negative and the post-baseline confirmatory ADA result is positive in the Nemolizumab treated group only.

Individual trough serum drug concentrations will be plotted over time in ADA-positive versus ADA-negative subjects.

This document is confidential.

13. Safety

All safety data will be summarized and listed on the SAF population.

Safety assessments will be conducted for all subjects at the baseline visit and at every subsequent visit. Safety will be assessed on the basis of AEs (including TEAEs, AESIs, and SAEs), physical examination and vital signs, clinical laboratory tests, electrocardiogram (ECG) and respiratory assessments. Summary of all safety endpoints will be presented for each treatment group.

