### Baseline Assessment

After signing the informed consent form (ICF), all subjects will be evaluated for study participation, based on eligibility criteria. The study assessments at the time of completion of the Week 52 visit from the PN LTE lead-in study RD.06.SPR.202699 will be used as baseline assessments for the current study.

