### 8.1 Inclusion Criteria

Individuals must meet all of the following criteria to be included in the study:

1. Subjects who achieved a clinical response at Week 52 of the LTE study RD.06.SPR.202699, defined as:
  - IGA score of 0 (clear) or 1 (almost clear)
  - AND
  - $\geq 4$ -point improvement in weekly average of PP NRS score from baseline of the lead-in study

*Note: Lead-in study baseline is defined as baseline PP NRS score in the Phase 3 studies RD.06.SPR.202685 or RD.06.SPR.203065 for subjects who rolled over into the LTE from these studies. For subjects who entered the LTE study from the Phase 2 study RD.03.SPR.115828, the baseline PP NRS score at entry into the LTE study RD.06.SPR.202699 will be used.*

2. Subjects with uninterrupted dosing of nemolizumab in the LTE study RD.06.SPR.202699 for 3 months before the Week 52 visit
3. Subjects willing and able to transfer into the study at the time of completion of the Week 52 visit in the LTE study RD.06.SPR.202699
4. Female subjects of childbearing potential (i.e., fertile, following menarche and until becoming postmenopausal unless permanently sterile) must agree to use an adequate and approved method of contraception throughout the study and for 12 weeks after the last study drug injection

Adequate and approved methods of contraception applicable for the subject and/or her partner are defined below:

- True abstinence, when in line with the preferred and usual lifestyle of the subject. Periodic abstinence (e.g., calendar, ovulation, symptothermal, post-ovulation methods) and withdrawal are not acceptable methods of contraception (see [Appendix 2](#)).
- Progestogen-only oral hormonal contraception

- Combination of male condom with cap, diaphragm, or sponge with spermicide (double barrier methods)  

Note: “Double barrier methods” refers to simultaneous use of a physical barrier by each partner. Use of a single barrier method (e.g., condom) with a spermicide is not acceptable.
- Combined (estrogen- and progestogen-containing) oral, intravaginal, or transdermal hormonal contraception
- Injectable or implanted hormonal contraception
- Intrauterine devices or intrauterine hormone-releasing system
- Bilateral tubal ligation or tube insert (such as the Essure system) at least 3 months before the study
- Bilateral vasectomy of partner at least 3 months before the study

5. Female subjects of non-childbearing potential must meet one of the following criteria:

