### 13.2 Immunogenicity Analysis

Blood samples will be collected at the time points indicated in the Schedule of Assessments ([Table 7](#)) and the clinical laboratory manual to assess anti-nemolizumab ADA.

The ADA will be determined by the designated CRO using a multi-tiered testing approach. A sensitive screening assay will first be used to assess clinical samples. Positive samples in the initial screening assay will be subjected to a confirmatory assay to demonstrate that ADA are specific for nemolizumab and not a result of non-specific interactions. Samples identified as positive in the confirmatory assay will be further characterized in 2 other assays, titering and neutralization antibody (Nab) assays.

Details related to the processing of serum samples and the assessments of ADA will be described in the bioanalytical plan, which will be finalized before the beginning of sample analysis. Results will be described in the bioanalytical report, which will be included as an appendix in the final clinical study report.

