*Clinical responder is defined as a subject with an Investigator Global Assessment (IGA) score= 0 or 1 and improvement in Peak Pruritus Numeric Rating Scale (PP NRS) score of ≥ 4 points from baseline of the lead-in study at Week 52 visit of the LTE study. Note: Lead-in study baseline is defined as baseline PP NRS score in the Phase 3 studies RD.06.SPR.202685 or RD.06.SPR.203065 for subjects who rolled over into the LTE from these studies. For subjects who entered the LTE study from the Phase 2 study RD.03.SPR.115828, the baseline PP NRS score at entry into the LTE study RD.06.SPR.202699 will be used.

** Relapse is defined as an increase in weekly average of PP NRS score ≥ 4 points from baseline or an increase in IGA score ≥ 2 from baseline at any point during the study. Subjects who relapse at any point during the treatment period or who complete through Week 24 are eligible for LTE re-entry.

Baseline Assessment

After signing the informed consent form (ICF), all subjects will be evaluated for study participation, based on eligibility criteria. The study assessments at the time of completion of the Week 52 visit from the PN LTE lead-in study RD.06.SPR.202699 will be used as baseline assessments for the current study.

Treatment Period

Eligible subjects will be randomized to receive either 1 or 2 injections of nemolizumab or placebo according to their dosage group in the LTE study, as assigned by interactive response technology (IRT). Study drug

This document is confidential.

will then be administered Q4W for 24 weeks with final dose administered at Week 20.

Refer to the below table for summary of the study treatment.

LTE Lead-in Study	Lead-in Study Assigned Treatment	Dose Q4W for 24 weeks ^a
RD.06.SPR.202699	Nemolizumab 30 mg (1 injection)	Blinded Nemolizumab 30 mg (1 injection)
		Blinded Placebo (1 injection)
	Nemolizumab 2 x 30 mg (2 injections)	Blinded Nemolizumab 2 x 30 mg (2 injections)
		Blinded 2 x Placebo (2 injections)

Abbreviation: LTE = long-term extension; Q4W = every 4 weeks.

^a Dose will be assigned based on dose received in LTE lead-in study

Clinical assessments will occur according to the Schedule of Assessments in the protocol through the Week 24 visit.

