8.2. Key Definitions

The 24-week **treatment period** is defined as Day 1/Baseline to Week 24. If early discontinued during treatment period, it is defined as the period until 4 weeks (<=28 days) after last dosing date or early termination date whichever is earlier.

The **Baseline value** is defined as the last non-missing value before the first dose of study drug. In case that the date of first injection is not available, the date of randomization is considered.

For diary data (PP NRS, SD NRS), the Baseline values will be week 52 value from LTE trial.

The **date of first treatment** is defined as the date of first injection of study drug.

The **date of last treatment** is defined as the date of last injection of study drug.

Study day is defined as the number of days from the date of first treatment (randomization date if not treated) and will be calculated as follows:

- If the event date \geq date of first treatment, then study day = event date – date of first treatment + 1. Treatment Day 1 is therefore defined as the day of first treatment.
- If the event date $<$ date of first treatment, then study day = event date - date of first treatment.
- If subject is randomized, but not treated, then study day = event date - date of randomization.

A subject's **date of last participation** in the trial is the last date of contact.

Only the **subjects infected by COVID-19** during study participation will be considered subjects with COVID-19 infection.

This document is confidential.

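### SAP 12's treatment-related ADA counts only new conversion since LTE Week 52, omitting earlier-induced ADA and titre rises, and its ng/mL unit for titre and NAb has no support in the assays described

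*SAP*

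**What the plan says.** SAP Section 12 defines the category in one sentence, limited to the nemolizumab group: "A treatment-related ADA is defined when the Baseline or confirmatory ADA result is negative and the post-baseline confirmatory ADA result is positive". It is to be tabulated by visit and dosing regimen.

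SAP 8.2 says that the Baseline value "is defined as the last non-missing value before the first dose of study drug". Protocol 7.1 (Baseline Assessment) gives the source of those values: the assessments at the "Week 52 visit from the PN LTE lead-in study RD.06.SPR.202699 will be used as baseline assessments for the current study". SAP 4.1 repeats this. Inclusion criterion 2 (Protocol 8.1) admits only "Subjects with uninterrupted dosing of nemolizumab in the LTE study RD.06.SPR.202699 for 3 months before the Week 52 visit".

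On sampling, SAP 12 says: "Blood samples to assess anti-Nemolizumab ADA will be collected at Baseline, Week 24 and Early Termination". On scale, it says: "The concentration of ADA titer (ng/mL) and neutralizing antibodies (ng/mL) will be summarized as continuous variables". SAP 5.3 lists ADA concentrations among the safety endpoints. Protocol 13.2 describes a screening assay and a confirmatory assay, after which confirmed positives "will be further characterized in 2 other assays, titering and neutralization antibody (Nab) assays". No readout or unit is given for any of these, and both documents leave assay detail to a bioanalytical plan.

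SAP 12 also plans a separate summary of the incidence of all positive ADA results at each visit.

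**The concern.** The label and the rule do not match. A reader who sees a treatment-related ADA percentage will take it as the share of subjects who mounted an antibody response to nemolizumab. The rule cannot deliver that, because its reference sample is drawn from people already being dosed. A subject who became ADA-positive in the lead-in or LTE study enters Baseline-positive and can never be counted, even if the titre climbs or the antibody becomes neutralising during these 24 weeks. Titres are measured on confirmed positives, so the data to show a boosted response would exist but have no category.

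The rule is also loosely worded. *Baseline or confirmatory* does not say which result at Baseline decides the classification, so two programmers could classify the same subject differently.

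The unit is a separate problem. A concentration in ng/mL is requested for titre and for NAb, yet the only assay in either document with an ng/mL readout is the drug-level ELISA (Protocol 13.1.2). A programmer has no described source for these values, and the SAP text does not ask for the NAb figure most readers want, the number of subjects positive.

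**Working it through.** The documents state no ADA rate, so there is no planned figure to reproduce. The check sets the passages side by side and then sizes the effect on stated assumptions.

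**What the rule counts**

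1. Reference sample: last value before the first dose in this study (SAP 8.2), taken from LTE Week 52 (Protocol 7.1, SAP 4.1).
2. Exposure at that sample: at least 3 months of uninterrupted nemolizumab in every entrant (Protocol 8.1, criterion 2).
3. Classification that follows:

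| Baseline ADA | Post-baseline ADA | Counted as treatment-related? |
|---|---|---|
| Negative | Confirmed positive | Yes |
| Positive | Positive, titre unchanged | No |
| Positive | Positive, titre risen | No |
| Positive | Positive, newly neutralising | No |

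**Size**

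Inputs from the documents: about 40 randomised 1:1 (Protocol 14.1, SAP 4.3), so 40/2 = 20 on nemolizumab. SAP 4.1 says about 100, which would give 100/2 = 50. One subject is 1/20 = 5 points, or 1/50 = 2 points.

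Assumed, not in the documents: *b*, the share positive at Baseline and still positive afterwards, from 0 to 15%; *p*, the conversion rate among Baseline negatives, set at 5%.

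- Counted rate = (1 − b) × p
- Any post-baseline positive = b + (1 − b) × p
- Gap = b, whatever the value of p
- Chance of at least one Baseline-positive among 20 = 1 − (1 − b)^20

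| b | Counted | Any positive | Gap (subjects of 20) | Chance of at least one |
|---|---|---|---|---|
| 0% | 5.00% | 5.00% | 0 | 0% |
| 5% | 4.75% | 9.75% | 5 points (1) | 64% |
| 10% | 4.50% | 14.50% | 10 points (2) | 88% |
| 15% | 4.25% | 19.25% | 15 points (3) | 96% |

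The gap is antibody induced by nemolizumab only if those subjects were negative before their first-ever dose. The documents do not show this either way.

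**Units**

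| Measurement | Assay described | Unit stated with the assay | Unit in SAP 12 |
|---|---|---|---|
| Drug level | ELISA, LLOQ 100 ng/mL (Protocol 13.1.2) | ng/mL | not applicable |
| ADA titre | Titering assay (Protocol 13.2) | none | ng/mL |
| NAb | Neutralisation assay (Protocol 13.2) | none | ng/mL |

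Protocol 5.2.2 reports earlier NAb findings as whether subjects developed it, that is, as a count.

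**The case against.** The strongest reply is that this is one sub-category in a fuller presentation. The incidence of all positive results at each visit is planned, and Baseline is a sampled visit, so subjects positive at entry are shown. Individual ADA and NAb results are listed (Listing 16.2.6.7), so a titre rise could be found by subject. A reader might infer from the definition that the trial's ADA rate as a whole will be understated. The documents do not support that; the effect is confined to the treatment-related row.

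The rule is also coherent as a within-study measure. Treatment-emergent adverse events are likewise counted from the first dose in this study, and the safety objective covers these 24 weeks rather than cumulative exposure. That stands, and it argues for correcting the label rather than merging two exposure periods into one figure.

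Protocol 5.2.2 describes low immunogenicity and no neutralising antibody in earlier subjects, so the gap may be nil. That stands too, although the same section compares ADA-positive with ADA-negative subjects in both PN and AD, so positives have been seen.

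On units, a reader might conclude that the titre and NAb summaries cannot be produced at all. That is not shown. Assay readouts are left to a bioanalytical plan outside these documents; titre can be summarised once its unit is right, and NAb can be tabulated according to its readout. Table 14.2.4.1 covers both, with no shell shown, so a NAb count may be intended. What remains is that the SAP text specifies a unit without a described source and no NAb count.

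**Conclusion.** The definition is wrong as labelled. It reports new conversion since LTE Week 52 under a name that implies response to nemolizumab, and it has no place for a boosted response. The understatement of that one row ranges from zero, if no subject is positive at entry, to about 5 percentage points for each Baseline-positive subject who stays positive at 20 per arm (2 points at 50). The 5 to 15% prevalences above are illustrations only. It would also be too strong to say that every entrant had a full uninterrupted year of nemolizumab; entry guarantees 3 months.

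The ng/mL unit for titre and NAb is unsupported by any ADA assay described, and needs aligning with the bioanalytical plan.

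The consequence is minor. ADA is summarised descriptively, and no efficacy result depends on it. The correction is still worth making, because it changes what the reported immunogenicity figure means and uses data the trial already plans to collect.

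**What to change.** In SAP 12:

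1. Rename the category *new-onset ADA since LTE Week 52*. State that the Baseline result decides it, with negative meaning either screening negative or screening positive but confirmatory negative.
2. Add a separate *boosted ADA* category for Baseline-positive subjects whose titre rises by a pre-stated fold, with the fold set from the bioanalytical plan before unblinding.
3. Summarise titre in the assay's own unit (median and range, confirmed positives only) and NAb as number and percent positive. Remove ng/mL from both, and correct the ADA concentrations entry in SAP 5.3 to match.

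Linking ADA results from before the first-ever nemolizumab dose is optional. The documents do not show that such results exist or are assay-comparable. Where they do and are, report them separately from within-study ADA.

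The cost is SAP wording and a little more tabulation, with no new samples and no change to conduct. The reported ADA figure may become slightly less favourable.

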13.1. Adverse Events

AEs will be coded using Medical Dictionary for Regulatory Activities (MedDRA) Version 24.1.

Treatment-emergent AEs (TEAEs), defined as those AEs occurring after the first administration of study treatment until the end of the follow-up period, will be tabulated in frequency tables by System Organ Class (SOC) and Preferred Term (PT) based on the MedDRA for treatment and follow-up periods. Missing date information will be handled using the algorithm described in [Section 8.3](#).

TEAEs during treatment period are defined as AEs with onset date on or after the first dose date till 4 weeks after the last treatment or early discontinuation date whichever is earlier. TEAEs during follow-up period are defined as AEs with onset date post treatment period (4 weeks after the last treatment or early discontinuation date, whichever is earlier) to follow-up visit date.

AEs will be summarized using the number and percent of subjects reporting each SOC and PT and sorted alphabetically by SOC and by descending frequency of PT within SOC.

Subjects who experienced multiple events within the same SOC will be counted once in the SOC summary. Subjects who experienced multiple occurrences of events with the same PT will be counted once in the PT summary.

When summarizing by causality or maximum severity, if a subject experiences more than 1 occurrence of the same AE, the occurrence with the greatest severity and the closest association with the study drug will be used in summary tables. TEAEs related to study drug/study procedure are those that are identified as reasonable possibility. If relationship or severity are missing, the event will be considered as AE related to study drug/study procedure or severe AE.

An AESI is a noteworthy treatment-emergent event for the study drug that should be monitored closely and reported promptly. An AESI can be either serious or non-serious. Based on the potential risks of Nemolizumab and the risks associated with biologics in general (i.e., class effects), the following AEs will be considered as AESIs:

- Injection-related reactions,
- Newly diagnosed asthma or worsening of asthma,

This document is confidential.

- Infections
- COVID-19 infections
- Peripheral edema: limbs, bilateral,
- Facial edema
- Elevated ALT or AST ($> 3 \times \text{ULN}$) in combination with elevated bilirubin ($> 2 \times \text{ULN}$).

The following summary tables for TEAEs will be presented for all TEAEs (i.e., TEAE all causalities) and study drug related TEAEs separately by treatment period and follow-up period.

- Overall Summary of TEAEs :
 - Overall summary table includes summary of subjects reporting TEAEs,
 - TEAE by maximum severity [Mild, Moderate, Severe]
 - TEAE related to study drug,
 - TEAE related to study drug by maximum severity [Mild, Moderate, Severe]
 - TEAE related to protocol procedure,
 - Serious TEAE,
 - Serious TEAE related to study drug,
 - TEAE of special interest,
 - TEAE leading to study drug interruption,
 - TEAE leading to study drug withdrawal,
 - TEAE leading to study discontinuation,
 - TEAE leading to death,
 - TEAE related to study drug leading to death
- TEAEs by SOC and PT
- Serious TEAEs by SOC and PT
- TEAEs by SOC, PT and Maximum Severity
- Severe TEAEs by SOC and PT
- TEAEs leading to study drug withdrawal by SOC and PT
- TEAEs leading to study discontinuation by SOC and PT

This document is confidential.

- TEAEs of special interest by category by SOC and PT
- TEAEs occurred in $\geq 5\%$ of subjects by SOC and PT
-
- Adjudicated TEAEs by SOC and PT
- TEAEs of Asthma and AESI reported by investigator with adjudication outcome by IAC
- Confirmed adjudicated TEAEs by SOC, PT and maximum severity
- TEAEs of special interest by category, SOC, PT and maximum severity

For overall study period which includes all periods (treatment and follow-up), the following summary tables will also be presented and repeated for all TEAEs (all causalities) and study drug related TEAEs.

- Overall Summary of TEAEs
- TEAEs by SOC and PT

For the subset of subjects with COVID-19 infection, the following summary tables will be provided additionally for all TEAEs and study drug related TEAEs, separately.

- Overall summary of TEAEs
- TEAEs by SOC and PT
- Serious TEAEs by SOC and PT
- TEAEs of Special Interest by category by SOC and PT

In addition, the exposure-adjusted incidence rate (i.e., number of subjects per 100 patient-years) will be summarized for all TEAEs (all causalities) and study drug related TEAEs during treatment period.

Exposure-adjusted incidence rates of TEAEs is defined as the number of subjects exposed to treatment and experiencing a certain event divided by the total time of all subjects who are at risk for the event. Specially, for subjects with no event the exposure time is the time from the first drug intake to the end of treatment period. Exposure years is calculated as last study drug exposure date minus first study drug exposure date plus one, divided by 365.25 which is the number of days count in a year. This exposure year calculated for each subject is then added cumulatively and is derived for each treatment arm. So each treatment arm will have one value for exposure years (also known as "patient years"). The exposure year calculation is different in case of subjects who have completed the study or discontinued from the study or having withdrawn from the study due to any reason. Only the event occurred during the treatment period will account for calculation.

Subject listings will be presented for all

This document is confidential.

- TEAEs,
- TEAEs of special interest,
- Serious TEAEs,
- Severe TEAEs,
- TEAE leading to permanent discontinuation of study drug,
- TEAEs leading to deaths.
- Pre-treatment AE

13.2. **Laboratory Evaluations**

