#### 6.1.2 Secondary Objective

To assess the safety of nemolizumab compared to placebo over a 24-week period in subjects with PN who previously responded to treatment in the LTE study

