**Table 3. Treatment Summary**

LTE Lead-in Study	Lead-in Study Assigned Treatment	Dose Q4W for 24 weeks a
RD.06.SPR.202699	Nemolizumab 30 mg (1 injection)	Blinded Nemolizumab 30 mg (1 injection)
	Nemolizumab 2 × 30 mg (2 injections)	Blinded Placebo (1 injection)
		Blinded Nemolizumab 2 × 30 mg (2 injections)
		Blinded 2 × Placebo (2 injections)

Abbreviation: LTE = long-term extension; Q4W = every 4 weeks.

aDose will be assigned based on dose received in LTE lead-in study.

Clinical assessments will occur according to the Schedule of Assessments in the protocol through the Week 24 visit.

If a subject meets the criteria for relapse at any point, the subject will exit the study and re-enter the LTE study (see [Figure 2](#)). Subjects who exit the study before Week 24 should complete an early termination (ET) visit. Subjects who complete the study through Week 24 are eligible to re-enroll in the LTE study.

Subjects who prematurely discontinue study drug for reasons other than relapse will be encouraged to complete the scheduled study visits. These subjects will only be eligible for re-enrollment in the LTE study if they continue with study visits through Week 24.

Subjects who discontinue the study for reasons other than relapse before Week 24 or who will not continue nemolizumab treatment in the LTE study should complete a follow-up visit, 12 weeks ( $\pm 7$  days) after the last study drug injection.

[figure not shown]

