### 9.6.2     Rescue Therapy

Rescue therapies are not permitted in this study. Subjects enrolled in this study have demonstrated a clinical response to nemolizumab; therefore, if a subject experiences relapse, they will be discontinued from this study and may be eligible to continue to receive nemolizumab by re-enrolling in the LTE study (see [Figure 2](#)).

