6.2. Safety Population

The safety population will comprise all randomized subjects who receive at least 1 dose of study drug. All safety data will be summarized based on the safety population under the treatment group “as treated”.

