	14.3.1.1.7	Overall Summary of Treatment Emergent Adverse Events (TEAEs) during Treatment Period, All Causalities	Safety Population – Subjects with COVID-19 Infection
	14.3.1.1.8	Overall Summary of Treatment Emergent Adverse Events (TEAEs) during Follow-up Period, All Causalities	Safety Population – Subjects with COVID-19 Infection
	14.3.1.1.9	Overall Summary of Treatment Emergent Adverse Events (TEAEs) during Treatment Period, Study Drug Related	Safety Population – Subjects with COVID-19 Infection
	14.3.1.1.10	Overall Summary of Treatment Emergent Adverse Events (TEAEs) during Follow-up Period, Study Drug Related	Safety Population – Subjects with COVID-19 Infection
	14.3.1.2.1	Treatment Emergent Adverse Events (TEAEs) during Treatment Period by SOC and PT, All Causalities	Safety Population
	14.3.1.2.2	Treatment Emergent Adverse Events (TEAEs) during Follow-up Period by SOC and PT, All Causalities	Safety Population
	14.3.1.2.3	Treatment Emergent Adverse Events (TEAEs) during Overall Study Period by SOC and PT, All Causalities	Safety Population
	14.3.1.2.4	Treatment Emergent Adverse Events (TEAEs) during Treatment Period by SOC and PT, All Causalities	Safety Population – Subjects with COVID-19 Infection
	14.3.1.2.5	Treatment Emergent Adverse Events (TEAEs) during Follow-up Period by SOC and PT, All Causalities	Safety Population – Subjects with COVID-19 Infection
	14.3.1.3.1	Treatment Emergent Adverse Events (TEAEs) during Treatment Period by SOC and PT, Study Drug Related	Safety Population

This document is confidential.

Header	Table Number	Name	Analysis Set
	14.3.1.3.2	Treatment Emergent Adverse Events (TEAEs) during Follow-up Period by SOC and PT, Study Drug Related	Safety Population
	14.3.1.3.3	Treatment Emergent Adverse Events (TEAEs) during Overall Study Period by SOC and PT, Study Drug Related	Safety Population
	14.3.1.3.4	Treatment Emergent Adverse Events (TEAEs) during Treatment Period by SOC and PT, Study Drug Related	Safety Population – Subjects with COVID-19 Infection
	14.3.1.3.5	Treatment Emergent Adverse Events (TEAEs) during Follow-up Period by SOC and PT, Study Drug Related	Safety Population – Subjects with COVID-19 Infection
	14.3.1.4	Exposure-Adjusted Incidence Rate for Treatment Emergent Adverse Events (TEAEs) during Treatment Period by SOC and PT, All Causalities	Safety Population

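### Relapse ends observation, probably sooner on placebo, yet serious, severe and special-interest events are compared between arms only as crude percentages

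*SAP*

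**What the plan says.** **Exit.** The text after Table 3 in Protocol 7.1 states: "If a subject meets the criteria for relapse at any point, the subject will exit the study and re-enter the LTE study". Protocol 9.6.2 repeats that "if a subject experiences relapse, they will be discontinued from this study", and SAP 4.1 carries the same rule.

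**Window.** SAP 13.1 counts treatment-period TEAEs from the first dose "till 4 weeks after the last treatment or early discontinuation date whichever is earlier".

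**Objective.** Protocol 6.1.2 sets a comparison between arms: "To assess the safety of nemolizumab compared to placebo over a 24-week period".

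**Statistic and denominator.** SAP 13.1: "AEs will be summarized using the number and percent of subjects reporting each SOC and PT". SAP 6.2: "The safety population will comprise all randomized subjects who receive at least 1 dose of study drug".

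**Exposure adjustment.** SAP 13.1 limits it to the treatment period and two groupings: the "exposure-adjusted incidence rate (i.e., number of subjects per 100 patient-years) will be summarized for all TEAEs (all causalities) and study drug related TEAEs". The table index (SAP section 17) lists two such tables. Table 14.3.1.4 is "Exposure-Adjusted Incidence Rate for Treatment Emergent Adverse Events (TEAEs) during Treatment Period by SOC and PT, All Causalities", and Table 14.3.1.5 is its drug-related counterpart. The index shows no exposure-adjusted version of the serious (14.3.1.6-7), severe (14.3.1.10-11) or AESI (14.3.1.16-17 and 14.3.1.26-27) tables.

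**Exposure definition.** SAP 13.1 gives two. One runs, for a subject without the event, from first drug intake to the end of the treatment period. The other is last dose date minus first dose date plus one day.

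**The concern.** Observation time in this study depends on the primary outcome. If withdrawal of nemolizumab brings more or earlier relapse, which is the effect the design sets out to measure, placebo subjects contribute less time in which an event can be recorded. A percentage of all treated subjects ignores that. With the same true event rate in both arms, the arm that stays longer shows the higher percentage.

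The plan recognises the issue for TEAEs overall but not for the events that weigh most in a benefit-risk reading. The SOC and PT rates fill part of the gap, since asthma, edema and COVID-19 correspond largely to preferred terms. They cannot isolate serious or severe events, or AESIs defined in Protocol 12.7.2 by criteria: infections that are severe or need long treatment, severe injection site reactions, and transaminase elevation combined with bilirubin elevation.

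**Working it through.** The documents give no relapse rate, event rate or power figure, so there is no stated result to reproduce. The size is worked out over an assumed range.

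**Inputs from the documents**
- Treatment period of 24 weeks, with visits every 4 weeks.
- About 40 subjects randomized 1:1, so 20 per arm (Protocol 14.1, SAP 4.3). SAP 4.1 says about 100.

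**Assumptions**
- Relapse by Week 24 (r): 5, 10 or 20% on nemolizumab and 40, 60 or 80% on placebo.
- Relapse hazard constant, with placebo relapse starting at once or after 8 weeks.
- Same constant event hazard in both arms, giving a 24-week true risk (p) of 5, 10 or 30%. The true ratio is therefore 1.00.
- No other dropout.

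**Formulas (exit at relapse, no lag)**
- Relapse hazard μ = −ln(1−r)/24; event hazard λ = −ln(1−p)/24.
- Mean observed time = r/μ weeks.
- Crude percentage = λ/(λ+μ) × [1 − (1−p)(1−r)].

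**One case: r = 10% v 60%, p = 10%**
- λ = 0.00439.
- Nemolizumab: μ = 0.00439; mean time 0.10/0.00439 = 22.8 weeks; crude 0.500 × (1 − 0.90×0.90) = 9.5%.
- Placebo: μ = 0.03818; mean time 0.60/0.03818 = 15.7 weeks; crude 0.1031 × (1 − 0.90×0.40) = 6.6%.
- Placebo/nemolizumab ratio 6.6/9.5 = 0.69. Gap at 20 per arm: 20 × (0.095 − 0.066) = 0.58 subjects.

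**Selected results at p = 10%**

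| Relapse, nemolizumab v placebo | Placebo lag | Ratio, exit at relapse | Ratio, exit at 4-weekly visit | Gap in subjects of 20 (at relapse / at visit) |
|---|---|---|---|---|
| 5% v 80% | none | 0.52 | 0.59 | 0.94 / 0.81 |
| 10% v 60% | none | 0.69 | 0.74 | 0.58 / 0.49 |
| 10% v 60% | 8 weeks | 0.82 | 0.86 | 0.35 / 0.26 |
| 20% v 40% | 8 weeks | 0.96 | 0.98 | 0.08 / 0.04 |

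**Whole range**
- Exit at relapse: mean observed time is 21.5-23.4 weeks on nemolizumab and 11.9-20.5 on placebo. The ratio is 0.51-0.96. At p = 5%, and again at p = 10%, the ratio is more than 10% below 1 in 16 of 18 settings.
- Exit at 4-weekly visits: the ratio is 0.58-0.98, and 14 of 18 settings exceed 10%.
- Gap at 20 per arm, exit at relapse: 0.04-0.47 subjects at p = 5% and 0.08-0.94 at p = 10%. For a common event (p = 30%) it reaches 20 × (29.3% − 15.6%) = 2.7.
- With equal relapse in the two arms the ratio is 1.00.

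**Would the planned rate formula repair this?** Take exit at the Week 4k visit without a dose there. The TEAE window is then 28k+1 days, but last dose minus first dose plus one is 28(k−1)+1 days. Exit at Week 4 credits 1 of 29 days, exit at Week 8 credits 29 of 57, and a completer 141 of 169. At 10% v 50% relapse and 25% event risk:
- Nemolizumab: 24.0% over a mean of 133.9 days, or 65.5 per 100 patient-years.
- Placebo: 19.4% over 101.3 days, or 70.1.
- Nemolizumab/placebo ratio: 65.5/70.1 = 0.93.

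With relapse of 10-20% v 30-80% (placebo always the higher) and event risks of 10, 25 and 50%, this ratio is 0.79-0.98. The error reverses and placebo looks worse. Dividing by observed days without stopping at the first event gives 0.93-1.00. If time at risk stops at the first event or the end of the window, expected first events equal λ × expected time at risk in each arm, so the ratio is 1.00.

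**The case against.** - **The effect is small and no test is affected.** No between-arm test of adverse events is planned, and the distortion for uncommon events is a fraction of a subject. This stands, and it limits the weight of the point. But the error has a direction, and descriptive tables are the only evidence offered for the safety objective.
- **The direction is assumed.** A reader might infer that the plan is bound to make placebo look safer. The documents do not support that: they state no relapse rate, and equal relapse gives no bias. The withdrawal design makes shorter placebo observation likely, no more.
- **The extreme ratio is unlikely.** The 0.51 figure needs 80% placebo relapse starting at once and exit at that moment. Protocol 5.2.2 gives a half-life of about 2 weeks, subjects enter as responders on uninterrupted dosing, and IGA is scored 4-weekly. The milder end of the range is more plausible.
- **AESIs are not wholly uncovered.** A reader might infer that special-interest events have no exposure-adjusted rate. That goes too far: the SOC and PT tables reach those that behave like preferred terms.
- **A crude percentage does not literally credit an early leaver with 24 event-free weeks.** It is a cumulative count within a window that closes at discontinuation. The problem is that the windows probably differ in length by arm.
- **Unequal observation is visible elsewhere.** SAP 9.1 and 9.6 report disposition, time to permanent discontinuation and treatment duration, and SAP 13.1 lists serious, severe and special-interest events individually. This helps a careful reader, but no planned output joins time to these events.

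**Conclusion.** The point holds in limited form. Serious TEAEs, severe TEAEs and AESI categories are compared as crude percentages although relapse probably shortens observation on placebo. If it does, and true rates are equal, nemolizumab shows somewhat more of these events only because its subjects stay longer. The size is a ratio of about 0.51-0.96 (exit at relapse) or 0.58-0.98 (exit at 4-weekly visits). That is less than one subject per event type at 20 per arm and 5-10% true risk. It rests on assumed relapse rates, constant hazards and no other dropout. If the figure of about 100 subjects in SAP 4.1 applied, the gaps would scale by 2.5, with the largest about 0.94 × 2.5 = 2.4 subjects.

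It would also be tempting to conclude that re-running the planned rate tables for more event types is enough. It is not: under the last-dose-minus-first-dose definition the correction overshoots, and Tables 14.3.1.4-5 share that defect. The point affects interpretation of the secondary objective, not the primary endpoint.

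**What to change.** 1. In SAP 13.1, replace the two exposure definitions with one time-at-risk rule: from first dose to the earliest of the first such event, study exit, or the end of the treatment-period TEAE window. Apply it to Tables 14.3.1.4 and 14.3.1.5 as well.
2. In SAP 13.1 and section 17, add treatment-period exposure-adjusted incidence rates by arm, on that rule, for serious TEAEs, severe TEAEs and each AESI category. Show them beside the crude number and percent, with observation time by arm.

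Cost: a few extra tables and one revised derivation, with no new data. The rates will be imprecise at about 20 subjects per arm and assume a roughly constant hazard. The change is best made before unblinding.
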